#### **6.2 Dose Modification during Consolidation Therapy**

- 6.2.1 If a dose reduction was required because of grade 3 or higher non-hematologic toxicity (except for febrile neutropenia/infection or constitutional symptoms) or if blood count recovery required > 56 days during induction therapy, the dose of CPX-351 during consolidation #1 will be reduced to 43 units/m^2/day.
- 6.1.3 If a subject experiences grade 3 or higher non-hematologic toxicity during consolidation #1 with the exception of febrile neutropenia/infection or constitutional symptoms or if blood count recovery required > 56 days during consolidation #1, the dose of CPX-351 will be reduced by 33% for consolidation #2 (that is, either 43 units/m^2/day X 2 doses or 30 units/m^2/day X 2 doses depending on dose used for consolidation #1).

#### **6.3 Dosing Comparisons of CPX-351**

CPX-351 (Prior Phase I study)

- 1 unit = 1.0 mg of cytarabine + 0.44 mg daunorubicin
- MTD: 100 units/m^2/day on Days 1, 3, and 5 for induction
- Cytarabine 100 units/m^2 = 100 mg/m^2
- Total Cytarabine administered for induction: 100 mg/m^2 X 3 days = 300 mg/m^2 total
- Daunorubicin 100 units/m^2=44 mg/m^2
- Total Daunorubicin administered for induction: 44 mg/m^2 X 3 days=132 mg/m^2 total

CPX-351 (Current Phase II study for HMA refractory or relapsed AML or MDS)

- 1 unit = 1.0 mg of cytarabine + 0.44 mg daunorubicin
- Dose for induction #1: 65 units/m^2/day on Days 1, 3, 5

- Cytarabine 65 units/m^2 = 65 mg/m^2
- Total Cytarabine administered for induction #1: 65 mg/m^2 X 3 days = 195 mg/m^2 total
- Daunorubicin 65 units/m^2 = 28.6 mg/m^2
- Total Daunorubicin administered for induction #1: 28.6 mg/m^2 X 3 days = 85.8 mg/m^2 total

## 7. ADVERSE EVENTS AND REPORTING PROCEDURES

### 7.1 Potential Adverse Events

There have been 3 completed trials of CPX-351: (1) Study 101, a phase I study of CPX-351 in patients with advanced leukemia and high risk MDS, (2) Study 204, a phase IIB multicenter, randomized study of CPX-351 versus 7+3 therapy in elderly patients with untreated AML between the ages of 60-75, (3) Study 205, a phase IIB multicenter randomized, open label trial of CPX-351 versus control salvage therapy in adult patients between the ages of 18-65 with AML in first relapse after initial CR > 1 month. We will summarize the adverse effects reported by Celator pharmaceuticals. Please additionally refer to the Celator pharmaceuticals investigators brochure.

#### Study 204

##### Overall Adverse Events for Study 204

The most common AEs of any severity following CPX-351 in Study 204 were: rash, diarrhea, nausea, febrile neutropenia, localized edema, constipation, pain, bacteremia, fatigue, decreased appetite, chills, cough, pyrexia, epistaxis, stomatitis, headache, petechie, insomnia, vomiting, pruritis, abdominal pain.

##### Grade 3-5 Adverse Effects with > 5% frequency with CPX-351 treatment in Study 204

Grade 3-5 Adverse effects with > 5% frequency in the CPX-351 arm from Study 204 include: febrile neutropenia, bacteremia, pneumonia, hypokalemia, neutropenia, sepsis, thrombocytopenia, diarrhea, acute renal failure, dyspnea, syncope, hypoxia, rash, clostridial infection, epistaxis, pain, fungal pneumonia, bacterial urinary tract infection.

CPX-351 Arm	7+3 arm
30 day mortality 3.5%	30 day mortality 7.3%
60 day mortality 4.7%	60 day mortality 14.6%
At least one grade 3 AE: 97.6% (83/85)	At least one grade 3 AE: 87.8% (36/41)
At least one grade 4 AE: 27.1% (23/85)	At least one grade 4 AE: 26.8% (11/41)
Grade 5 AE (Death): 11.8% (10/85)	Grade 5 AE (Death): 17.1% (7/41)
Grade 5 bleeding events: 3/85 (fall, intracranial hemorrhage, respiratory tract hemorrhage)	Grade 5 bleeding events: 0% (0/41)
Febrile neutropenia grade 3 and 4: 63.5% (54/85)	Febrile neutropenia grade 3 and 4: 51.2% (21/41)
Bacteremia grade 3 and 4: 35.3% (30/85)	Bacteremia grade 3 and 4: 19.5% (8/41)
Fungal infection Grade 3 and 4 : 15.4% (13/85)	Fungal infection Grade 3 and 4: 0%
Grade 3 rash: 8.2% (7/85)	Grade 3 rash: 0% (0/41)

**Study 204: Grade 3-5 Cardiac Events**

Preferred Term/Event	Grade 3 and 4 AE		Grade 5 AE	
	CPX-351 (N=85) N	7+3 (N=41) N	CPX-351 (N=85) N	7+3 (N=41) N
Atrial Fibrillation	3	1	0	0
Cardiac Failure	2	1	0	0
Tachycardia (SVT)	1	1	0	0
Angina Pectoris	0	1	0	0
Cardiac Arrest	0	0	0	1
Myocardial Infarction	1	1	0	1
Restrictive cardiomyopathy	1	0	0	0
Acute myocardial infarction	0	1	0	0
Myocarditis	0	1	0	0
Troponin increased	1	0	0	0

**Study 205**

**Grade 3-5 Adverse Events > 5% frequency with CPX-351 from Study 205**

Grade 3-5 Adverse effects with > 5% frequency in the CPX-351 arm from Study 205 include: febrile neutropenia, bacteremia, pneumonia, sepsis, fatigue, hypokalemia, urinary tract infection, rash, pyrexia, neutropenia, syncope, septic shock.

**Grade 5 Adverse Events in Study 205**

There were a total of 19 grade 5 events in the CPX-351 arm. Grade 5 events include 4 deaths from pneumonia, 4 deaths from sepsis, 2 deaths from AML, 2 deaths from septic shock, 1 death from acute respiratory failure, 1 death from respiratory distress, 1 death from respiratory failure, 1 death from cardio-respiratory arrest, 1 death from cerebral hemorrhage, 1 death from subdural hematoma, 1 death from sudden cardiac death. There were 9 deaths in the control salvage arm.

**Adverse Event Incidence (any grade) in all patients treated with CPX-351 at a dose of 100 units/m^2**

The CPX-351 investigator’s brochure reviews the adverse event incidence of any grade in all patients treated with CPX-351 at a dose of 100 units/m^2 (N=196). The most common adverse events of any grade with > 15% frequency include (in rounded percentages):

- Rash – 66%
- Fever & Infection (Febrile Neutropenia) - 57%
- Nausea - 57%
- Diarrhea - 50%
- Pain - 45%
- Constipation - 44%
- Fatigue - 43%
- Bacteria in the blood (Bacteremia) - 37%
- Fever (Pyrexia) - 36%
- Chills - 36%

- Swelling □Localized edema□□- 33%
- Decreased Appetite - 33%
- Vomiting - 32%
- Cough - 32%
- Headache - 31%
- Shortness of Breath (Dyspnea) - 26%
- Nosebleed (Epistaxis) - 26%
- Mouth Swelling (Stomatitis) - 25%
- Low Potassium Levels (Hypokalemia) - 25%
- Small Red or Purple Skin Spots (Petechiae) - 24%
- Dizziness - 22%
- Hypotension - 22%
- Pneumonia - 22%
- Anxiety - 22%
- Abdominal Pain - 21%
- Insomnia - 21%
- Itching (Pruritus) - 20%
- Fast Heart Rate (Tachycardia) – 16%
- Weakness (Asthenia) – 15%
- Swelling of Limbs (Edema Peripheral) – 15%
- Hypertension – 15%
- In some cases, side effects can be serious, long lasting, or may never go away. There is also a risk of death.

### **Effects on Mutagenicity, Carcinogenicity, Impairment of Fertility, Pregnancy, Nursing Mothers**

Mutagenicity, carcinogenicity, and impairment on fertility with CPX-351 have not been conducted. Cytarabine is known to cause extensive chromosomal damage. As reviewed in the investigator's brochure, Daunorubicin has been reported to cause fibrosarcomas, adenocarcinomas, and peritoneal sarcomas. Given the mutagenicity of daunorubicin and cytarabine, patients undergoing treatment with CPX-351 will be advised to use a reliable contraceptive method. CPX-351 has not been studied in pregnant animals. Both Cytarabine and Daunorubicin have been designated as Pregnancy Category D due to known teratogenicity. It is not known if CPX-351 is excreted in human milk. Given possible drug excretion in human milk and because of possible serious adverse risks in nursing infants, patients receiving CPX-351 should not breast feed. Given the advanced age of patients in this study, we do not anticipate any women in this study to be pregnant in this study, be

of child-bearing age, or be breast-feeding. Men in this study are still at risk of mutagenicity of spermatozoa. Therefore all patients will be advised to use a reliable contraceptive method.

### **SUMMARY: Discussion of Adverse Effect Profile of CPX-351**

In summary, the risk and side effect profile of CPX-351 has been found to be comparable to that of traditional induction therapy with 7+3 (study 204) and control salvage therapy (study 205). There is an increased incidence of febrile neutropenia, bacteremia, and fungal infections with CPX-351, which is thought to be consistent with the longer duration of myelosuppression with CPX-351 given its pharmacokinetics. Though infections were common, deaths from infections were not common, indicating effective supportive care.

In terms of 60-day mortality, the CPX-351 arms in Study 204 and Study 205 had lower or similar 60-day mortality compared to the control arms respectively (4.7% vs 14.6% in Study 204; 14.8% vs 15.9% in Study 205).

### **Risk Reduction**

Given the anticipated older patient population in our study cohort of patients with HMA refractory or relapsed AML or MDS, with possible risks of prolonged myelosuppression given older age and underlying MDS in patients with MDS or AML secondary to MDS, we are dose reducing CPX-351 in our study to 65 units/m^2/day on Days 1, 3, and 5 for initial induction therapy.

## **7.2 Adverse Event Reporting**

Adverse events will be graded according to CTCAE v4.0. Both Serious and Non-Serious Adverse Events will be clearly noted in source documentation and listed on study specific Case Report Forms (CRFs). The Protocol Director (PD) or designee will assess each Adverse Event (AE) to determine whether it is unexpected according to the Informed Consent, Protocol Document, or Investigator's Brochure, and related to the investigation. All Serious Adverse Events (SAEs) will be followed until resolution to  $\leq$  grade 1, or until 4 weeks after the last dose of the study treatment, or until other therapy is initiated for AML, whichever comes first.

Patients with unresolved AEs after 4 weeks will have the events classified as permanent sequelae.

## **7.3 Serious Adverse Event Reporting Instructions**

The investigator must complete the Serious Adverse Event Report Form in English, assess the relationship to study treatment and send the completed form by fax within 24 hours to Celator and to the local IRB Office. The original and the duplicate copies of the Serious Adverse Event Form, and the fax confirmation sheet must be kept with the case report forms.

Follow-up information is sent to Celator or its designee as well as the local IRB office via the original Serious Adverse Event Form, re-stating the date of the original report. Either a new Serious Adverse Event Form is sent (stating that this is a follow-up), or the original one resent (with the new information highlighted and a new date provided). The follow-up should describe whether the event has resolved or continues, if and how it was treated, whether the patient continued or discontinued study participation. The form and fax confirmation sheet must be retained.

### **7.3.1 Reporting Serious Adverse Events to Regulatory Agencies and Review Boards**

The need for an expedited report to regulatory authorities will be determined by the Sponsor-Investigator. All AEs that are serious, unexpected and associated with the use of CPX-351 will be reported to the Food and Drug Administration (FDA) by the Sponsor-Investigator.

### **7.3.2 Report of Adverse Events to the Institutional Review Board**

The Sponsor-Investigator will report serious adverse events to the Stanford Institutional Review Board (IRB) per institutional policy.

### **7.3.3 Investigator Reporting to the FDA**

Serious adverse events (SAEs) that are unlisted/unexpected, and at least possibly associated to the drug, and that have not previously been reported in the Investigators brochure, or reference safety information document should be reported promptly by the principal investigator to the Food and Drug Administration (FDA) by telephone or by fax. Fatal or life threatening SAEs that meet the criteria for reporting to the FDA must be reported to the FDA within 7 calendar days after awareness of the event. All other SAEs that meet the criteria for reporting to the FDA must be reported to the FDA within 15 calendar days after awareness of the event. A clear description of the suspected reaction should be provided along with an assessment as to whether the event is drug or disease related.

### **7.3.4 Adverse event updates/IND safety reports**

Celator shall notify the Investigator via an IND Safety Report of the following information:

- Any AE associated with the use of study drug in this study or in other studies that is both serious and unexpected.
- Any finding from tests in laboratory animals that suggests a significant risk for human subjects including reports of mutagenicity, teratogenicity, or carcinogenicity.

The Investigator shall notify his/her IRB/EC promptly of these new serious and unexpected AE(s) or significant risks to subjects.

The Investigator must keep copies of all AE information, including correspondence with Celator and the IRB/EC, on file.

## **7.4 Adverse Event Definition based on CTCAE v4.0 criteria**

An Adverse Event is any untoward medical occurrence (any symptom, sign, or abnormal lab/radiology/pathology finding) in a patient administered with a pharmaceutical product and which does not necessarily have to have a causal relationship with this treatment, only temporal association. This is inclusive of worsening of pre-existing conditions or any increases in the frequency of a pre-existing condition. As previously described in other CPX-351 protocols, there is a difference between seriousness and severity that should be clarified:

- Severe is used to describe the intensity of a specific event; the event itself may of varying medical significance
- Serious relates to patient or event outcome that is associated with the patient's life or functioning

### **7.4.1 Definition of Serious Adverse Event based on CTCAE v4.0 criteria**

A serious adverse event (SAE) is any adverse event that at any dose:

- Results in Death
- Is life threatening
- Requires prolongation of existing hospitalization\*
- Results in persistent or significant disability or incapacity

- Is a congenital anomaly/birth defect
- Is an important medical event#

\*Hospitalization itself will not be considered a serious adverse event if required for complications of AML or co-morbid conditions. Hospitalization will be considered SAE if it fulfills the criteria for a serious and unexpected adverse event as otherwise described.

\*Exceptions to the definition of SAE are myelosuppression and associated complications (Ex. uncomplicated febrile neutropenia, infection, grade 1-3 bleeding events (with or without platelet transfusions)). These are common and expected events in patients with AML and MDS. These events will be reported as AEs, not SAEs. Hospitalizations for routine procedures, investigations, and chemotherapy administration are not considered an SAE in this protocol.

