APPENDIX H: ANTHRACYCLINE EQUIVALENCE TABLE

APPENDIX I: 2008 WHO CLASSIFICATION OF AML

APPENDIX J: 2008 WHO CLASSIFICATION OF MDS

APPENDIX K: PATIENT STUDY CALENDAR

APPENDIX L: STUDY DRUG RE SUPPLY FORM

**PROTOCOL SYNOPSIS** .....

TITLE	A Phase 2 Study of CPX-351 for treatment of AML and higher risk MDS relapsed or refractory to prior therapy with Hypomethylating (HMA) agent
STUDY PHASE	Phase 2 Study
INDICATION	Treatment of older patients with AML or Higher Risk MDS, relapsed or refractory to HMA therapy
INVESTIGATIONAL PRODUCT	CPX-351
PRIMARY OBJECTIVE(S)	
1) Determine the efficacy of CPX-351 in study population. Outcome measure: response rate (CR + CRi)
 
2) Determine the safety of CPX-351 in study population. Outcome measure: Safety Data (30 and 60 day mortality, SAEs, Grade 3-5 AE frequency)
 
Study Population: Subjects age 60 and older with:
 
1) higher risk MDS who are refractory or relapsed after prior HMA therapy
 
2) Subjects with MDS who are HMA relapsed or refractory who have progressed to AML
 
3) AML with refractory/relapsed disease after prior HMA therapy

SECONDARY OBJECTIVE(S)	
1) Determine the duration of remission
 
2) Determine overall survival at 12 months
 
3) Determine the early induction mortality at Day 60 after 1st induction

TREATMENT SUMMARY	
Up to 2 courses of induction therapy are allowed. First Induction: CPX-351 at a dose of 65 units/m^2/day, on Days 1, 3, and 5; Second Induction: CPX-351 at a dose of 65 units/m^2/day on Days 1 and 3;
 
Up to 2 courses of post-remission therapy are allowed: CPX-351 at a dose of 65 units/m^2/day, on Days 1 and 3.

SAMPLE SIZE	33
STATISTICAL CONSIDERATIONS	Simon 2-stage minimax design being used to determine the sample size and optimizing identification of early effect.

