### **CPX-351 Administration**

CPX-351 is administered through a peripheral or central venous access, over approximately 90-minute infusions. The doses of CPX-351 are calculated using the patient's actual weight. Both inpatient and outpatient administration of CPX-351 is permitted.

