# Medical and scientific judgment should be exercised in deciding whether expedited reporting is appropriate in situations where none of the outcomes listed above occurred. Important medical events that may not be immediately life-threatening or result in death or hospitalization but may jeopardize the patient or may require intervention to prevent one of the other outcomes listed in the definition above should also usually be considered serious. Examples of such events include allergic bronchospasm requiring intensive treatment in an emergency room or at home or convulsions that do not result in inpatient hospitalization, or the development of drug dependency or drug abuse. A new diagnosis of cancer during the course of a treatment should be considered as medically important.

Non-hematologic SAEs CTCAE Grade 3 and above, and all subsequent follow-up reports will be reported to the Stanford Cancer Center Data and Safety Monitoring Committee (DSMC) using the study specific CRF regardless of the event's relatedness to the investigation. Following review by the DSMC, events meeting the IRB definition of 'Unanticipated Problem' will be reported to the IRB using eProtocol within 10 working days of DSMC review, or within 5 working days for deaths or life-threatening experiences.

AEs that do not meet the requirement for expedited reporting will be reported to the IRB as part of the annual renewal of the protocol.

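### The SAE list in 7.4.1 omits new inpatient hospitalization, and neither the footnote nor the important-medical-event clause closes the gap, so SAEs risk under-ascertainment and uneven classification

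*Combined protocol and SAP*

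**What the plan says.** Section 7.4.1 lists six criteria that make an adverse event serious: death, threat to life, a hospitalization criterion, disability, birth defect and important medical event. The hospitalization criterion reads "Requires prolongation of existing hospitalization". Initial admission is not on the list.

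The asterisk on that bullet leads to notes that limit or restore hospitalization:

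- Disease and co-morbidity: "Hospitalization itself will not be considered a serious adverse event if required for complications of AML or co-morbid conditions".
- Conditional inclusion: "Hospitalization will be considered SAE if it fulfills the criteria for a serious and unexpected adverse event as otherwise described".
- Myelosuppression and its complications, with uncomplicated febrile neutropenia, infection and grade 1-3 bleeding as examples: "These events will be reported as AEs, not SAEs".
- Planned stays: "Hospitalizations for routine procedures, investigations, and chemotherapy administration are not considered an SAE in this protocol".

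The important-medical-event note then covers "Important medical events that may not be immediately life-threatening or result in death or hospitalization but may jeopardize the patient".

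SAEs are part of a primary objective. The Protocol Synopsis gives "Outcome measure: Safety Data (30 and 60 day mortality, SAEs, Grade 3-5 AE frequency"), and Section 10.1 repeats the three components. On setting, Section 4.1 states: "Both inpatient and outpatient administration of CPX-351 is permitted".

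**The concern.** The list and the text around it do not agree on whether admission makes an event serious. Someone who classifies from the list alone will not mark a new admission as serious. Someone who classifies from the surrounding notes may.

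Two things are at stake. The first is the SAE component of the primary safety outcome. The second is the flow of safety information. SAE status triggers the 24-hour form to the drug supplier and the IRB (Section 7.3), the report of non-hematologic SAEs of grade 3 and above to the Data and Safety Monitoring Committee (DSMC; Section 7.4.1), and that committee's regular SAE review (Section 11.2). Events that need no expedited report reach the IRB only at annual renewal. Section 4.3 allows the trial to stop for unacceptable toxicity but sets no numeric boundary, so the committee depends on what reaches it as an SAE.

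**Working it through.** No arithmetic applies, because the plan states no expected SAE or admission rate. The check sets the texts side by side.

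**1. Does the rest of 7.4.1 presuppose an admission criterion?** Yes.
- The important-medical-event note speaks of outcomes already listed and names hospitalization beside death. Hospitalization as such is not listed.
- One of its examples is convulsions that do not lead to admission. The example makes sense only if convulsions that do lead to admission are already serious.
- The exclusions for planned stays are needed only if other admissions count.

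This points to a drafting omission.

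**2. Does the footnote supply the criterion?** No. It counts a hospitalization when the event meets the criteria described elsewhere, but those criteria contain no admission item, so the rule is circular. It also requires the event to be unexpected. Section 7.2 has expectedness assessed for each adverse event against the consent form, the protocol or the Investigator's Brochure. Sections 7.3.1 and 7.3.3 then combine it with seriousness to decide FDA reporting. There it is a reporting attribute and does not define seriousness.

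**3. Does the added condition matter?** Yes. Section 7.1 lists diarrhea, acute renal failure, dyspnea, syncope, hypoxia and rash among the grade 3-5 events above 5% frequency with CPX-351 in Study 204. Because the protocol lists them, they are expected under Section 7.2. None is named in the myelosuppression exception.

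**4. Applying the text as written:**

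| Event | Already an inpatient, stay lengthened | Outpatient, newly admitted |
|---|---|---|
| Life-threatening, not myelosuppressive | SAE by its own bullet | SAE by its own bullet |
| Uncomplicated febrile neutropenia | AE by the exception | AE by the exception |
| Attributed to AML or co-morbidity, no other criterion met | Stay does not count, by the footnote | Stay does not count, by the footnote |
| Expected, non-myelosuppressive, not fatal, life-threatening or disabling | SAE by the prolongation bullet | No bullet met; SAE only if judged an important medical event |

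Only the last row differs by setting. Its middle cell takes the prolongation bullet at face value. Because the asterisk sits on that bullet, the unexpectedness condition could be read as limiting prolonged stays too, which is a further reason to rewrite the note.

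**5. What is still captured?** Appendix E places an event for which admission is indicated at grade 3. Such events should therefore enter the Grade 3-5 frequency. Section 7.2 puts serious and non-serious events on the case report forms (CRFs), and Section 12.4.2 totals all recorded events. Deaths are counted separately. What can be lost is the SAE label and the reporting that depends on it.

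**The case against.** The strongest reply is that 7.4.1 does not exclude new admissions. The footnote says hospitalization will count under a condition, the exclusions imply that some admissions count, and the important-medical-event clause gives the investigator a way to classify a worrying admission as serious. The exclusions bind inpatients as well, so the gap is narrow. The Grade 3-5 frequency recovers most of the information.

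Much of this stands, and it rules out several stronger readings that a reader might infer:

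- **That a drug-caused admission can never be an SAE.** The documents do not say so. They leave it to judgment, where a lengthened stay is covered by a bullet.
- **That the SAE count is in fact too low.** The documents give no rate of admissions that meet no other criterion. If all 33 planned patients are treated, one patient whose only SAE is missed moves the proportion of patients with an SAE by 1/33 = 3.0 percentage points. That is a unit of measure and says nothing about how often it would happen.
- **That the Study 204 cardiac table shows the size of the gap.** It pools grades 3 and 4, grade 4 events are life-threatening and already serious, and it records no admissions.
- **That count recovery takes place outside hospital.** Only outpatient dosing is stated. Section 4.1 and Appendix K schedule assessments during recovery without naming a setting.

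The reply does not remove the contradiction. The important-medical-event clause depends on judgment and is written around events that may not lead to admission. Tabulating grade 3-5 events at analysis does not replace a 24-hour report or a committee report during the trial.

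**Conclusion.** The concern holds as an internal inconsistency in the definition of a primary safety component. For one class of event (expected, non-myelosuppressive admissions that are not fatal, life-threatening or disabling), SAE status rests on individual judgment and can depend on whether the patient was already in hospital. The consequence is a risk of under-ascertainment and uneven classification of SAEs, and of missed 24-hour and committee reports. A proven undercount is not shown.

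The size cannot be estimated from the documents. The conclusion assumes that staff apply the list and footnote literally and that some patients are outpatients when toxicity occurs, which the protocol permits. The Grade 3-5 frequency should still include these events, and 30- and 60-day mortality is unaffected. The exception for myelosuppression and infection is a separate, explicit choice and would limit SAE counts even after the correction. The point should be corrected, because the definition is wrong as written and the repair is small.

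**What to change.** Reconcile the list, the footnote and the important-medical-event note in 7.4.1:

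1. Extend the hospitalization bullet so that it covers inpatient admission as well as prolongation of a stay.
2. Remove unexpectedness from the footnote, and leave it to the reporting rules in 7.2, 7.3.1 and 7.3.3.
3. State in one place which exclusions remain: procedures, investigations and chemotherapy stays; the listed myelosuppression events; and AML complications and co-morbidity. Say that each applies equally to new and prolonged admissions. The AML and co-morbidity exclusion needs this most, because in patients aged 60 and older it could otherwise absorb drug-related events.
4. Carry the revised definition into the CRF guidance. If patients have already been treated, reclassify their recorded events under it so that the SAE count follows one rule.

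The cost is a short protocol amendment and a CRF note, somewhat more SAE forms, and a slightly less favourable SAE count. The design, sample size and response analysis do not change.

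### Section 7.4.1 does not say whether a fatal or life-threatening infection remains an SAE; the AE window and the AE counting rule also need minor tidying

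*Combined protocol and SAP*

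**What the plan says.** The list of SAE criteria in 7.4.1 includes "Results in Death", "Is life threatening" and "Requires prolongation of existing hospitalization". Only the last carries an asterisk. One of the asterisked notes below the list then reads "Exceptions to the definition of SAE are myelosuppression and associated complications (Ex. uncomplicated febrile neutropenia, infection, grade 1-3 bleeding events", calls such events common and expected in AML and MDS, and concludes "These events will be reported as AEs, not SAEs". Febrile neutropenia is limited to the uncomplicated kind and bleeding to grades 1-3. Infection has no explicit limit.

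Several things depend on SAE status:
- Section 10.1 lists SAEs as a primary safety measure, beside 30/60-day mortality and grade 3-5 AE frequency.
- Section 7.3 requires an SAE form within 24 hours to the drug supplier and the IRB office.
- The end of 7.4.1 sends non-hematologic SAEs of grade 3 or higher to the DSMC, and 11.2 has the DSMC review SAEs regularly.
- AEs that do not need expedited reporting reach the IRB at annual renewal.

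Two further passages bear on the AE summary. Section 4.1 (End of Active Treatment Phase) stops AE collection once at least 30 days have passed since the last dose and other therapy has begun. Section 10.1.2, to which 12.4 refers for the time-frame, stops at 4 weeks after treatment or at new therapy, whichever is earlier. Section 12.4.2 sets the total number of each adverse event against the number of patients and has no once-per-patient rule.

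**The concern.** Two people applying 7.4.1 to the same death from sepsis during neutropenia could classify it differently, one from the outcome criteria and the other from the note. In a 33-patient trial with SAEs as a primary measure, a few such cases would change the result. They would also change what the supplier, the IRB and the DSMC see promptly.

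Infection is where this matters most. For the Study 205 CPX-351 arm, section 7.1 reports: "There were a total of 19 grade 5 events in the CPX-351 arm". It goes on: "Grade 5 events include 4 deaths from pneumonia, 4 deaths from sepsis, 2 deaths from AML, 2 deaths from septic shock".

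The window and the counting rule are smaller matters. They affect only the descriptive AE summary, including grade 3-5 AE frequency.

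**Working it through.** **1. The two rules side by side.** Take an infection that complicates myelosuppression and is fatal.
- Outcome criteria in 7.4.1: it results in death, so it is an SAE.
- Note in 7.4.1: it is a complication of myelosuppression and an infection, so it is an AE and not an SAE.

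No sentence gives an order of precedence. The 5-working-day IRB timeline for deaths and life-threatening experiences, later in 7.4.1, does not settle it. That timeline follows DSMC review, and the reporting route to the DSMC starts from SAE status.

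**2. What does not depend on the answer.**
- An excepted infection is still an AE, so it is recorded on the CRF (7.2) and counts in grade 3-5 AE frequency.
- 30/60-day mortality is counted from the first dose (10.1.4), whatever the SAE status.
- The sample size has no safety input. With p0 = 0.20, pA = 0.40, 18 patients then 15, and stopping at 4 or fewer of 18, the exact two-stage binomial calculation reproduces N = 33. One-sided alpha is 0.0458 and power 0.801, using a final cut-off of more than 10 of 33, which is derived here and not stated in the plan.

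**3. Fatal infections (illustrative; dose and population differ).**
- Study 205 grade 5 events (7.1): 4 + 4 + 2 + 2 + seven single events = 19, as stated. Pneumonia, sepsis and septic shock: 4 + 4 + 2 = 10, and 10/19 = 52.6%. How many arose during myelosuppression is not given.
- Study 204 grade 5 rate (7.1): 10/85, so 33 × 10/85 = 3.9 patients.
- With an infection share of 1/4 (5.1.7 describes 4 CPX-351 deaths in Study 204, one of them from pneumonia): 3.9 × 1/4 = 1.0.
- With the Study 205 share: 3.9 × 10/19 = 2.0.
- Study 205 alone: the arm size is not given. A 2:1 split of 125 is about 83, so 78-88 is assumed: 33 × 10/88 = 3.8 to 33 × 10/78 = 4.2.
- Range: about 1 to 4 of 33.

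**4. Life-threatening events.** Appendix E describes grade 4 as life threatening. For Study 204, 7.1 gives "At least one grade 4 AE: 27.1% (23/85" patients) on CPX-351. Then 33 × 23/85 = 8.9 patients with any grade 4 AE, all event types together. This is an expected count: the 95% binomial range is 4 to 14, and the chance of more than 9 is 0.40. The share due to infection is not given.

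**5. Minor: AE window.** Take a patient who has induction 1 only, with the last dose on Day 5.
- Section 4.1 cannot stop before Day 5 + 30 = 35.
- Section 10.1.2 stops on Day 5 + 28 = 33 if the 4 weeks run from the last dose. If new therapy starts on Day 20 (assumed), it stops on Day 20, and the gap is 35 − 20 = 15 days.
- The 30 ± 3 day toxicity visit falls on Days 32-38. With the stop on Day 33, Days 34-38 (5 of the 7 allowed days) lie outside.
- If the 4 weeks run instead from discontinuation after the Day 14 ± 3 marrow (Days 11-17), they end on Days 39-45. Then no allowed visit day lies outside unless new therapy starts.

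**6. Minor: counting.** Suppose 12 of 33 patients have a given event (assumed). With 1, 1.5 or 2 episodes each (assumed), the literal ratio is 12/33 = 36.4%, 18/33 = 54.5% or 24/33 = 72.7%. The share of patients affected is 36.4% throughout.

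**The case against.** The case for the narrow reading is good. The asterisk sits on the hospitalization criterion, while death and threat to life carry no mark. The other two examples are limited to lesser events, and the word restricting febrile neutropenia may also be meant to govern infection. Calling the events common and expected fits poorly with deaths, and 7.4 ties seriousness to the patient's life or functioning. All of this stands, and it makes a narrow intent plausible. It does not close the gap, because the note presents itself as an exception to the SAE definition as a whole and not to one criterion.

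It is also fair to say that the consequences are limited. A reader might infer that septic deaths would vanish from the safety results. The documents do not support that: such deaths stay in the CRFs, in grade 3-5 AE frequency and, within their windows, in 30/60-day mortality. Nor would FDA expedited reporting generally change. Sections 7.3.1 and 7.3.3 confine it to unexpected events, and 7.1 already lists pneumonia, sepsis and bacteremia as known. Section 4.3 allows stopping for unacceptable toxicity but does not tie this to SAE status, so no effect on stopping can be shown.

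On the minor points, collecting AEs for longer than they are analysed is not in itself an error. In 12.4.2 the gloss about the rate in the study population makes patient incidence a plausible intent. Both passages still need a clear rule.

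**Conclusion.** The gap in 7.4.1 is real and should be closed. Read literally, a fatal or life-threatening infection complicating myelosuppression is not an SAE; read narrowly, it is. The plan does not choose. The effect is confined to the SAE measure, the 24-hour form, and DSMC receipt and review.

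The size is about 1 to 4 fatal infections in 33 patients. This rests on rates carried over from Studies 204 and 205, an assumed infection share and an assumed Study 205 arm size. A reader might take about 9 of 33 as an upper limit for life-threatening infections. It is not one: it is the expected number of patients with a grade 4 AE of any kind at the Study 204 rate. This trial uses a lower dose but enrols patients in whom HMA therapy has failed, with no upper age limit, so Study 204 does not bound the rate in either direction. Grade 4 is also only a proxy for the seriousness criterion.

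The window and counting points are correct but minor; neither carries a decision rule.

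**What to change.** **Main change, 7.4.1.** State that the exception for myelosuppression and its complications does not apply to any event that results in death or is life threatening, and that such events are counted as SAEs and sent to the DSMC. The cost is a few more SAE forms.

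**Minor changes.**
- Reconcile 4.1 and 10.1.2 into one AE-onset window, name it as the analysis window, and make it include the 30-day visit. Flag AEs with onset after new therapy, since these are harder to attribute. The rules in 7.2 and 4.1 on following existing events to resolution can stay separate.
- In 12.4.2, report for each event the number and percentage of treated patients with at least one occurrence, at worst grade. Total event counts may be added. This is a wording change only.
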